8.2 Overview of statistical methods

Descriptive statistics (mean, SD, median, interquartile range, range, counts, and percentage) will be used to describe and compare (t-test or rank sum test for continuous variables and Fisher's exact test for categorical variables) baseline characteristics between the historical control group and PGx arms.

8.2.1 Implementation Endpoint(s):

- We will report the number and proportion of tests returned prior to the first dose of chemotherapy.
- We will report the proportion of dose modifications made in agreement with genotype-guided dosing recommendations at the first dose.
- The proportion of tests ordered compared to the number eligible for testing.

8.2.2 Secondary Endpoint(s):

1. Clinical endpoints

- a. The proportion of patients experiencing severe TRAEs will be compared in the PMBB historical control group vs. the PGx group using Fisher's exact test.

Subgroup analyses will be performed by tumor type.

- b. The relative dose intensity (RDI) will be calculated for 5-FU, capecitabine or irinotecan as the cumulative administered dose divided by the anticipated cumulative dose over the first 6 cycles. RDI will be compared in the PMBB historical control group vs. the PGx group using linear regression adjusted for sex, race, BMI, tumor type, cancer stage, line of therapy and ECOG performance status.

Subgroup analyses will be performed by tumor type.

2. Patient reported outcomes

Patient reported outcomes as assessed on a Likert scale will be reported as means (SD) and compared between the PMBB historical control group vs. the PGx group using linear regression adjusting for age, sex, race, tumor type, cancer stage, BMI, line of therapy, and ECOG performance status.

3. Patient attitudes toward PGx testing

Patient knowledge and attitudes towards PGx testing will be assessed on a Likert scale will be reported as means (SD). We will compare results by sex, race, tumor type, and insurance status by using linear regression. (See survey in Appendix 14.7)

8.2.3 Tertiary Endpoint(s):

1. Clinical endpoints in minority populations

The proportion of patients experiencing severe TRAEs will be compared in the PMBB historical control group vs. the PGx group using Fisher's exact tests, stratified by race.

2. Minor allele frequencies will be reported by ancestry for the DPYD and UGT1A1 genes.
3. Medical services utilization and costs

We will obtain data from Data Analytics Center (DAC) on service utilization and costs. These will include: number of physician visits; number of emergency department visits; number of hospitalizations; length of hospital stay; number of emergency department and hospital admissions associated with drug-related adverse events; DPYD and UGT1A1

genetic testing costs; physician visit cost; emergency department visit costs; hospitalization costs; inpatient and physician-administered medication costs; and total costs. Care Everywhere will be utilized to obtain information if patients received care outside Penn Medicine. Additionally, medical records will be requested for admissions that occur outside of Penn Medicine.

We will compare utilization and costs incurred by the PMBB usual care group with utilization and costs incurred by the PGx group using Poisson regression methods (for number of visits), and linear regression methods with appropriate transformations (e.g., log-transform, winsorization) to account for skewness in utilization and cost distributions.

4. Survival Analysis

Overall survival and progression free survival at approximately six months will be compared between the PMBB historical control group vs. the PGx group by use of Kaplan-Meier estimators and log-rank tests. Cox proportional regression analysis will be performed to adjust for clinical covariates including age, sex, race, tumor type, cancer stage, BMI, and ECOG performance status.

5. Pre-treatment uracil and fluoropyrimidine associated toxicity

First, we will examine the range of pre-treatment uracil concentrations with the association of severe toxicity to determine if there is a cut-off whereby toxicity occurs. Previous studies have proposed uracil $> 16\text{g/ml}$ as highly predictive for severe toxicity, but we will validate this cut-off in our patient population.¹⁵ We will also examine whether the pre-treatment uracil levels vary in *DPYD* variant carriers. Second, we use logistic regression models to determine the risk of severe toxicity including a binary factor for uracil concentration (above and below cut-off), with adjustment for age, sex and treatment regimen.

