Secondary Endpoints:	
 1. The proportion of patients experiencing severe treatment related adverse events (TRAEs) over the first six cycles of chemotherapy. [Time Frame: 6 cycles] 2. The relative dose intensity of 5-FU and irinotecan dosing over the first six cycles. [Time Frame: 6 cycles] 3. Patient reported outcomes (PROs) during the first six cycles of chemotherapy. [Time Frame: 6 cycles] 4. Patient knowledge about and attitudes towards PGx. [Time Frame: 6 months] 5. The incidence of patients of African ancestry experiencing TRAEs over the first six cycles of chemotherapy. [Time Frame: 6 cycles] 6. The frequency of actionable DPYD and UGT1A1 in various ancestry groups. [Time Frame: 6 months] 7. PFS and OS in patients after genotyping [Time Frame: 6 ± 2 months] 8. The costs of PGx-guided chemotherapy [Time Frame: 6 cycles]
Study Population:	
Inclusion criteria
 
 1. Male and female subjects, 18 years or older at time of study 2. Pathologically confirmed gastrointestinal malignancy for which treatment with a fluoropyrimidine and/or irinotecan is indicated 3. Able and willing to provide informed consent 4. Willing to undergo blood or saliva sampling for PGx testing and comply with all study-related procedures 5. Life expectancy of at least 6 months 
Exclusion criteria
 
 1. Prior treatment with irinotecan 2. DPYD or UGT1A1 genotype already known

	
 3. Severe renal or hepatic impairment (or unacceptable laboratory values) 4. Women who are pregnant or breast feeding, or subjects who refuse to use reliable contraceptive methods throughout the study 5. Treating physician does not want subject to participate
Phase:	N/a
Description of Sites/Facilities	
Penn Medicine sites:
 
 1. Perelman Center for Advanced Medicine (PCAM) 2. Penn Presbyterian Medical Center (PPMC) 3. Lancaster General Hospital (LGH)
Enrolling Participants:	Approximately 500-800 participants will be enrolled across the Penn Medicine sites.

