
 1. To determine if chemotherapy-induced toxicity differs by ancestry group. 2. To determine the frequency of actionable DPYD and UGT1A1 in various ancestry groups. 3. To determine if PGx testing influences progression-free (PFS) and overall survival (OS). 4. To determine the cost-effectiveness of PGx guided chemotherapy dosing. 5. To determine the association of pre-treatment plasma uracil concentrations with severe (Grade 3 to 5) fluoropyrimidine induced toxicity with the first dose. 	
 1. The proportion of patients experiencing a serious treatment relate adverse event during the first six cycles of chemotherapy stratified by self-reported ancestry. 2. Minor allele frequency of variants in DPYD and UGT1A1 reported by self-reported ancestry. 3. PFS and OS in patients at 6 ± 2 months. 4. Means and variances of cost in the genotype-guided group as compared to the historical control group (Costs of hospitalizations, treatment, PGx test, medical services) 5. Pre-treatment plasma uracil concentrations as measured by HPLC.

OBJECTIVES	ENDPOINTS
Optional Microbiome Substudy at PCAM only	
1. To determine whether the microbiome composition impacts the occurrence of chemotherapy-induced adverse events	1. The change in bacterial abundance as measured by operational taxonomic units (OTUs) 2. The change in bacterial composition or beta diversity as measured by weighted UniFrac distance

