5.4 Participant recruitment

Approximately 1000 cases of GI cancer are treated annually at PCAM, 150 cases at PPMC, and 200 at LGH. Roughly 100 unique patients receive fluoropyrimidine and/or irinotecan-based chemotherapy regimen in a typical month at the PCAM GI cancer clinic. Based on the frequency of *DYPD* and *UGT1A1* variants and the number of GI cancer patients seen within Penn Medicine, we anticipate that testing 500-800 patients in this multisite study would result in 45-70 patients with the actionable genotypes (see Table 4). Approximately 20% of the GI cancer population at Penn Medicine is of African ancestry. All recruitment will be done through the Penn cancer centers and treating oncologists. Clinic schedules will be screened by the clinical research coordinator for new patients with GI cancer being evaluated for treatment. Prior to the scheduled visit, the research coordinator will notify the treating oncologist about potential eligible participants and remind them of the study. The treating oncologist will discuss the study with the patient during the evaluation visit and consent will be obtained by the treating GI oncology provider (physician or advanced practice provider) or the research coordinator. This will occur in person or by remote consent. Patients will be given a copy of the official informed consent form and an opportunity to ask questions. Patients will be given sufficient time to consider participating in the trial.

Participants who complete the patient questionnaire regarding attitudes towards PGx testing will receive a \$25 gift card. The Greenphire ClinCard will be used to disburse funds and mailed to the patient.

Women of childbearing potential who are pregnant or breastfeeding will not be recruited into this study due to the risk of fetal harm caused by exposure to 5-FU, capecitabine, or irinotecan and the potential for serious adverse reactions in breastfed infants. A pregnancy test is not routinely performed in these patients at Penn Medicine thus will not be included as a study procedure.

Table 4. Anticipated study initiation and estimated participant accrual across sites

Calendar year	Q1 2021	Q2 2021	Q3 2021	Q4 2021	Q1 2022	Site totals
Site						
PCAM (20/mo)	60	60	60	60		240
PPMC (10/mo)		30	30	30	30	120
LGH (20/mo)		60	60	60	60	240
Total						600

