		
proportion of patients with TRAEs were compared between the prospective and historical control groups among UGT1A1 poor metabolizers. Chi-square tests were used for all comparisons. Factors contributing to having a TRAE were evaluated using a multivariable logistic regression model adjusting for age, sex, race, tumor type, ECOG score, presence of metastases, intent of treatment, DPYD phenotype, and UGT1A1 phenotype using a stepwise approach.
 
 d. Relative dose intensity for fluoropyrimidines and irinotecan, defined as cumulative dose administered divided by the anticipated cumulative dose over six cycles reported as mg/m² was compared between variant carriers and wild-type patients (or PM vs. IM/NM for irinotecan) in the prospective cohort using t-tests. Relative dose intensity for fluoropyrimidines and irinotecan, was compared between the prospective and historical control groups in variant carriers (or PM for irinotecan) using t-tests. e. Patient reported outcomes (PROs) during the first six cycles of chemotherapy were compared in the prospective cohort between DPYD variant carriers and wild-type patients using chi-square tests in the subset that completed PROs. f. Patient knowledge and attitudes towards PGx testing were evaluated using chi-square and t-tests as appropriate.
Missing data	28	
 a. Prospective completion of chemotherapy related toxicity per the National Cancer Institute-Common Terminology Criteria for Adverse Events (NCI-CTCAE) was not feasible due to a lack of a consistent research coordinator throughout the study. In addition, the completion rate for the PROs was very low therefore we could not assign a grade to the adverse event. b. Revised definition severe toxicities from \geq Grade 3 toxicities to treatment related adverse events requiring treatment in the hospital, emergency department, or oncology evaluation center.

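### The ancestry objective asks whether toxicity differs between groups, but the analysis assigned to it compares the two cohorts within each race

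*Combined protocol and SAP*

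**What the plan says.** Protocol section 3 states tertiary objective 1 as "To determine if chemotherapy-induced toxicity differs by ancestry group". The matching endpoint is the proportion of patients with an event "during the first six cycles of chemotherapy stratified by self-reported ancestry"; it names no contrast. The synopsis (section 1.1) carries a related item among the secondary endpoints, "The incidence of patients of African ancestry experiencing TRAEs over the first six cycles of chemotherapy", with no comparator group.

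The analysis is in protocol section 8.2.3 item 1, under a heading about minority populations. The proportions with severe TRAEs are to be compared between the PMBB historical controls and the PGx cohort by Fisher's "exact tests, stratified by race".

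The SAP lists no ancestry outcome (item 26). Its TRAE comparisons (item 27, 2c) are DPYD carriers against wild-type, UGT1A1 poor metabolizers against the rest, and prospective against historical patients within those genotype groups. Race enters once, in a "multivariable logistic regression model adjusting for age, sex, race, tumor type, ECOG score, presence of metastases, intent of treatment" and the two genotype phenotypes, fitted "using a stepwise approach".

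**The concern.** The objective concerns a difference between ancestry groups. The planned tests hold race fixed and ask whether the two cohorts differ. That is a legitimate question about the effect of testing within each group, but it is a different estimand, and no result of those tests estimates the ancestry difference. A stratified test pooled over race would not help either, because it conditions race out.

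Two things are at stake. If section 8.2.3 is followed as written, the stated objective ends without an effect estimate or interval. The within-race p-values also come from strata of very different size, so someone looking for a difference between groups could read a significant result in the larger stratum and a non-significant one in the smaller as a finding about ancestry.

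**Working it through.** **The plan's own figure.** No precision or power is stated for the ancestry objective. The only power figures are in Table 5 (section 8.1), for PMBB against PGx among carriers. Full binomial enumeration of the two-sided Fisher test at 0.05, 60% against 30%, gives 0.839 at 54 per group and 0.800 at 48, matching the table's 83.9% and 80%. Table 5 is sound for that contrast, which is not this one.

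**Can the planned tests see an ancestry difference?** A constructed example, with 100 and 400 patients per cohort (20% and 80% of 500):
- African ancestry: 60/100 with a severe TRAE in PMBB and 60/100 in PGx. Fisher p = 1.0.
- All others: 120/400 in PMBB and 120/400 in PGx. Fisher p = 1.0.
- The objective's own question, within PGx: 60/100 against 120/400. Fisher p = 5 × 10⁻⁸.

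Both planned tests are null although the groups differ by 30 points.

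**Can stratum p-values be compared instead?** The same 60% against 30% cohort effect gives:
- 10 per cohort (6/10 against 3/10): p = 0.37.
- 40 per cohort (24/40 against 12/40): p = 0.013.

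The effect is identical and only the stratum size differs.

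**What could a direct comparison deliver?** Inputs: 500-800 patients tested (section 8.1), and "Approximately 20% of the GI cancer population at Penn Medicine is of African ancestry" (section 5.4), which gives 100 against 400 up to 160 against 640. The severe TRAE rate p is an assumption, because the documents give none by ancestry. Unadjusted 95% half-width = 1.96 × √[p(1−p)/n₁ + p(1−p)/n₂].
- p = 0.30, 100 and 400: 1.96 × √(0.21/100 + 0.21/400) = 0.100.
- p = 0.30, 160 and 640: 1.96 × √(0.21/160 + 0.21/640) = 0.079.
- p = 0.20 (numerator 0.16): 0.088 and 0.069.
- p = 0.40 (numerator 0.24): 0.107 and 0.085.

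Power (normal approximation for two proportions, two-sided 0.05, rate in the larger group 20-40%):

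| Difference | N = 500 | N = 600 | N = 800 |
|---|---|---|---|
| 10 points | 43-51% | 50-60% | 62-73% |
| 15 points | 77-85% | 84-91% | 93-97% |

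A direct estimate is therefore useful, but power is adequate only for differences of about 15 points or more.

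**The case against.** The strongest reply is that the SAP does contain something close to the missing comparison. Its logistic model of factors contributing to a TRAE includes race, and SAP item 16 says confidence intervals on the odds of a severe TRAE were reported. A reader might infer from section 8.2.3 that the trial never compares ancestry groups, or that the SAP has no ancestry analysis at all. The documents do not support that: if race survives selection, an adjusted race odds ratio will exist. What remains is that stepwise selection may drop race, the model is not tied to this objective, and it also carries the DPYD and UGT1A1 phenotypes. Table 1 shows variant frequencies differing by ancestry (for example 0.0001 against 0.012 for c.557A>G, and 0.024 against 0.003 for HapB3), so genotype may be part of why the groups differ. A race term adjusted for it is not the overall difference.

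Second, the mismatch may lie in the objective's wording. The section 8.2.3 heading and the synopsis endpoint both fit a question about whether testing helps minority patients. That is fair. It is a reason to keep the within-race comparisons and add to them, or to reword the objective, but the objective as it stands still has no matching contrast.

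Third, the stratified tables would show proportions by race side by side, so it goes too far to say that the trial cannot speak to the question. What is missing is a named contrast with an interval. Nor does any section say that p-values will be compared across strata; that misreading is a risk and not a plan.

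A reader might also infer that the within-race test rests on a handful of DPYD carriers of African ancestry. Section 8.2.3 item 1 refers to patients and is not restricted to carriers, and the plan's actionable group includes UGT1A1, so no such count follows.

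**Conclusion.** The concern holds as a wrong contrast for a tertiary objective. The assigned analysis tests cohort within race, specifies neither a between-ancestry comparison nor an ancestry-by-cohort interaction, and can return p = 1.0 in every stratum when the groups differ by 30 points. The SAP's stepwise model might yield a race odds ratio but does not assure one.

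A direct comparison on the planned sample would have an unadjusted 95% half-width of about 10 points at 500 patients and 8 at 800. This rests on an assumed TRAE rate near 30% (7 to 11 points over 20-40% and both sample sizes), a 20% African-ancestry share among those enrolled, and planned rather than achieved numbers. Adjustment will change it somewhat.

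The point is minor. Section 3 ranks the objective as tertiary, although the synopsis lists a related item as secondary, and the feasibility and main toxicity conclusions do not depend on it.

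**What to change.** Add to section 8.2.3 item 1, and to the SAP, a between-ancestry comparison of severe TRAE in the prospective cohort:
- Use logistic regression with self-reported ancestry forced in and exempt from stepwise selection, adjusted for age, sex, tumor type, stage, regimen and ECOG.
- Report the odds ratio and the standardised risk difference, each with 95% CI. Fit the model first without genotype phenotype, which addresses the objective, and then with DPYD and UGT1A1 phenotype as a secondary model.
- Keep the within-race PMBB against PGx comparisons as a separate question. Assess whether the PGx effect varies by a cohort-by-ancestry interaction with its interval, not by comparing stratum p-values.
- Use one term throughout. The endpoint says self-reported ancestry and the analysis says race.

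The cost is one extra model, plus the interaction term. Race/ethnicity, the chemotherapy course and TRAEs are already among the data to be collected (protocol sections 7.4 and 7.5). SAP item 14 places all analyses in May-June 2024; if they are done, label the model as added after the plan. The alternative is to state that tertiary objective 1 was not formally addressed.

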8 STATISTICAL PLAN

8.1 Sample size

For the implementation aims, the sample size is based on average GI oncology clinical volume and anticipated number of patients that are eligible for testing. We anticipated testing 500-800 patients during the course of the study at the three Penn Medicine sites. No hypothesis testing will be performed.

For the effectiveness aims, we hypothesize that the chemotherapy-related severe TRAEs will decrease from 60% in the variant carriers receiving full dose chemotherapy in the historical control group enrolled into the PMBB to 30% in variant carriers receiving genotype guided chemotherapy.¹⁸ The following table presents the power for different sample sizes per group and different expected proportions experiencing severe TRAEs in the PGx group, based on two-sided Fisher's exact test at the alpha level of 0.05 (Table 5). Based on the frequencies of *DPYD* and/or *UGT1A1* in the population (~10%), testing 500 patients in each group will result in ~50 patients with actionable genotypes.

Table 5. Power estimate for the reduction in Severe TRAEs with PGx testing

Toxicity rate	39% in PGx	35% in PGx	30% in PGx
N in each group with actionable variants			
18	17.8%	24.8%	35.6%
36	32.3%	45.8%	63.6%
48			80%
54	49.4%	66.3%	83.9%
70		80%	
72	67.4%	82.9%	
97	80%		

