10.2 Risk/Benefit Assessment

10.2.1 Known Potential Risks

Blood will be drawn from all participating patients for determining the genotype prior to start of chemotherapy. Risks of venipuncture include possible bruising, infection at the site, and in rare cases, fainting. These risks are minimized by using trained personnel. The impact on clinical oncologic outcomes is unknown. Chemotherapy dose adjustments will be performed by the treating oncologist according to his or her clinical judgment.

There can also be a risk in knowing genetic information. New health information about inherited traits that may affect participating patients and or their blood relatives may be found during the research study. DPD deficiency is an autosomal recessive disease; carriers usually do not have related health problems, but they do have an increased risk of complications when treated with fluoropyrimidine therapy.²³ *UGT1A1* plays a role in the metabolism of bilirubin and is associated with hereditary hyperbilirubinemia syndromes. The *28 variant is a common cause of Gilbert syndrome.⁶ Individuals with Gilbert syndrome may experience transient elevations in unconjugated plasma bilirubin in response to various triggers (e.g., fasting, infection, or medications). Genotypes most implicated in Gilbert syndrome are *UGT1A1**28/*28 and *UGT1A1**6/*6. Crigler-Najjar syndrome type I is very rare and results from deleterious

UGT1A1 mutations that results in hyperbilirubinemia and occur early in childhood therefore the PGx testing is unlikely to result in incidental findings. However, identification of a heterozygous state may have implications for prenatal genetic counseling. The treating oncologist may choose to return these incidental findings if pertinent for clinical care. For the purposes of this current study, variants in the *UGT1A1* gene will be interpreted to guide irinotecan drug dosing.²⁴

Additionally, there is the risk of loss of privacy with storing the health and genetic data of participating patients. Very rarely health or genetic information could be misused by employers or insurance companies; however, in such events, patients may have difficulty finding or maintaining a job or insurance. Laws such as the federal Genetic Information Non-Discrimination Act (GINA) prohibit employers and health insurers from discriminating against individuals based on their genetic information. However, GINA does not protect against life insurance or long-term care insurance.

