Additional analyses	29	
 a. The number of treatment modifications (i.e., delay of treatment or dose reduction) and treatment discontinuations in the prospective cohort were compared between the DPYD variant carriers vs DPYD wild-type patients using chi-square tests. These outcomes were also compared between the prospective and historical control groups among DPYD variant carriers. These analyses were also performed for the UGT1A1 phenotype. b. Overall survival at one year was reported for the prospective and historical cohorts.
Harms	30	No harms of the genotyping intervention were reported.
Statistical software	31	SAS version 9.4 and R version 4.2.3
References	32	
 1. Henricks LM, Lunenburg CATC, De Man FM, et al. DPYD genotype-guided dose individualisation of fluoropyrimidine therapy in patients with cancer: a prospective safety analysis. The Lancet Oncology. 2018;19(11):1459-1467. doi:10.1016/S1470-2045(18)30686-7 2. Amstutz U, Henricks LM, Offer SM, et al. Clinical Pharmacogenetics Implementation Consortium (CPIC) Guideline for Dihydropyrimidine

		
Dehydrogenase Genotype and Fluoropyrimidine Dosing: 2017 Update. Clin Pharmacol Ther. 2018;103(2):210-216. doi:10.1002/cpt.911
 
3. Fresenius Kabi. Fluorouracil Prescribing Information. Food and Drug Administration. February 2024. Accessed May 1, 2024. https://www.accessdata.fda.gov/drugsatfda_docs/label/2024/040279s030lbl.pdf
 
4. Genentech. Xeloda Prescribing Information. Food and Drug Administration. December 2022. Accessed May 1, 2024. https://www.accessdata.fda.gov/drugsatfda_docs/label/2022/020896s044s045s046s047s048s049s050s051lbl.pdf
 
5. Pfizer. Camptosar Prescribing Information. Food and Drug Administration. January 2022. Accessed May 1, 2024. https://www.accessdata.fda.gov/drugsatfda_docs/label/2022/020571Orig1s053lbl.pdf

--	--	--

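### PFS and OS are compared only in whole cohorts, where about 10% of patients have a genotype-driven change in recommended dosing, so a null result says little about efficacy in dose-reduced patients

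*Combined protocol and SAP*

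**What the plan says.** Protocol 8.2.3(4), Survival Analysis: "Overall survival and progression free survival at approximately six months will be compared between the PMBB historical control group vs. the PGx group". The methods are Kaplan-Meier curves, log-rank tests and a Cox model. The listed Cox covariates are clinical and demographic, with no genotype term and no genotype-by-group term. Section 3 gives the objective as whether PGx testing influences PFS and OS.

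SAP item 29b: "Overall survival at one year was reported for the prospective and historical cohorts". It gives no test, no carrier stratum and no PFS.

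The SAP's other clinical contrasts between the prospective and historical groups are restricted. Severe TRAEs (item 27, 2c), relative dose intensity (item 27, 2d) and treatment modifications and discontinuations (item 29a) are compared among DPYD variant carriers or UGT1A1 poor metabolizers.

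On the share affected, Protocol 8.1 says "testing 500 patients in each group will result in ~50 patients with actionable genotypes" and Protocol 5.4 says "testing 500-800 patients in this multisite study would result in 45-70 patients with the actionable genotypes". Table 2 leaves DPYD normal metabolizers and UGT1A1 normal and intermediate metabolizers at the standard starting dose. On efficacy, Protocol 10.2.1 says: "The impact on clinical oncologic outcomes is unknown".

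**The concern.** The test can affect survival mainly through patients whose recommended dose it changes. Toxicity, where benefit is expected, is examined in those patients. Survival, where a cost of giving less drug would appear, is examined in a population in which roughly 83-90% have no genotype-driven change. A loss of efficacy in carriers is therefore averaged with a large majority in whom none is expected. Two similar curves, or two similar one-year figures, would be compatible with a substantial loss in carriers, and a reader could easily miss that.

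**Working it through.** **1. The plan's own power figure.** The only power calculation is for severe TRAEs among carriers: the rate "will decrease from 60% in the variant carriers receiving full dose chemotherapy in the historical control group" "to 30% in variant carriers receiving genotype guided chemotherapy", two-sided Fisher's exact test "at the alpha level of 0.05". Exact enumeration at 48 per group gives 80.05%, against 80% in Table 5. The toxicity calculation is sound and is made in carriers. No event count or power is given for survival.

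**2. Share with a changed recommendation.**
- Stated: 50/500 = 10%; 45/500 = 9.0%; 70/800 = 8.8%.
- Upper bound from Table 1 under Hardy-Weinberg, with HapB3 counted once and unreported frequencies set to zero. European ancestry: DPYD alleles sum to 0.0372, so carriers = 1 − (1 − 0.0372)² = 7.3%; UGT1A1 poor metabolizers = (0.316 + 0.008)² = 10.5%; either = 17.0%. African ancestry: DPYD sum 0.021, carriers 4.2%; poor metabolizers (0.373 + 0.004)² = 14.2%; either = 17.8%.
- With 20% African ancestry (5.4) and the rest treated as European: 0.8 × 17.0 + 0.2 × 17.8 = 17.2%. This requires every patient to receive both drug classes. With half on irinotecan it is 11.9%.

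**3. Dilution.** The documents give no survival rates or effect sizes, so the following are assumptions: six-month event-free probability S0 of 0.90, 0.65 or 0.50; carrier HR of 2; exponential times; no dropout; full adherence; no drift between cohorts. With share f:

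S1 = (1 − f)·S0 + f·S0^HR; diluted HR = ln S1 / ln S0; events D = N(2 − S0 − S1); Schoenfeld power = Φ(√D/2 · ln HR − 1.96).

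Example with f = 0.10, S0 = 0.65, N = 500: S1 = 0.585 + 0.1 × 0.4225 = 0.627; diluted HR = 0.4664/0.4308 = 1.083; D = 500 × 0.7228 = 361; power = Φ(0.755 − 1.96) = 11%.

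| Share | S0 | Diluted HR | Events | Schoenfeld power | Simulated log-rank power | Non-significant (simulated) |
|---|---|---|---|---|---|---|
| 10% | 0.90 | 1.095 | 104 | 7% | 7% | 93% |
| 10% | 0.65 | 1.083 | 361 | 11% | 11% | 89% |
| 10% | 0.50 | 1.074 | 512 | 13% | 14% | 86% |
| 17% | 0.90 | 1.163 | 108 | 12% | 13% | 87% |
| 17% | 0.65 | 1.142 | 369 | 25% | 27% | 73% |
| 17% | 0.50 | 1.128 | 521 | 28% | 30% | 70% |

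Simulation used 2,000 runs per row. At these diluted HRs, 80% power needs about 1,400 to 6,200 events. At 800 per group, simulated power is 9-19% (10% share) and 17-41% (17% share).

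**4. Sensitivity to the effect, 500 per group.** Carrier HR 1.5: simulated power 5-13%. Carrier HR 3: Schoenfeld power 14-24% at 10% and 31-56% at 17%.

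**5. The carrier contrast.** Fifty per group, HR 2: expected events 50(2 − S0 − S0²) = 14.5, 46.4 and 62.5; Schoenfeld power 26%, 66% and 78% (simulated 24%, 64% and 76%). The 95% CI factor exp(1.96 × 2/√D) is ×/÷ 2.80, 1.78 and 1.64. As a one-year yardstick (neither text plans this test), 70% vs 55% OS, with 45, 50 or 70 carriers per group, gives exact-enumeration chi-square power of 31.5%, 34% and 45%.

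**6. Drift.** If the PGx-era baseline hazard were 20% lower (assumed) and the carrier HR were 2, simulated whole-cohort trials at 500 per group showed significant apparent benefit in 5-35% and significant harm in at most 1%.

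**The case against.** The strongest reply is that the stated objective concerns testing, not dose reduction. A testing policy acts on everyone tested, and its effect is properly averaged over non-carriers. That stands: the whole-cohort contrast is a legitimate estimand, and the carrier analysis is an addition to it.

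Second, the protocol uses the same group wording for TRAEs in 8.2.2(1a), although 8.1 powers that comparison in carriers. Within the protocol, survival is therefore not singled out. The asymmetry is in the SAP, where survival is only descriptive. This also stands, so the log-rank figures apply to 8.2.3(4) alone, while the missing carrier stratum applies to both texts.

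Third, at the documents' counts the carrier contrast would often be non-significant too. True, which is why it should be reported as an estimate.

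A reader might go further and infer that a finding of no difference is almost guaranteed. The documents do not support that. It is a fair description only near the 10% share with a moderate effect. At 17% and HR 3, about 44-69% of trials would be non-significant, and drift against historical controls can produce a significant difference in the wrong direction. Nor do the documents say that a null survival result will be taken as proof of preserved efficacy: they set no margin and call the oncologic impact unknown. The risk lies in how the result may be read.

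**Conclusion.** The concern holds as a gap in the analysis, not as an error in the whole-cohort comparison. With about 10% of patients affected, a doubled hazard in carriers becomes a whole-cohort HR of 1.07-1.10; at the 17% bound it is 1.13-1.16. With 500 per group, the 8.2.3(4) log-rank would miss it in about 86-93% and 70-87% of trials respectively. A null result there is weak evidence about the patients who received less drug. These figures rest on assumed survival rates and hazard ratios, 500 historical controls, full adherence and no drift. Less than full adherence would dilute the effect further. Restricting to carriers removes the dilution, but it does not remove small numbers or historical-control bias.

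**What to change.** In Protocol 8.2.3(4) and SAP item 29b:

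- Add PFS and OS, prospective vs historical, among patients with an actionable genotype on the relevant drug: DPYD variant carriers on a fluoropyrimidine, and UGT1A1 poor metabolizers on irinotecan. Report a hazard ratio or survival difference with its 95% CI, to be read as an estimate and not as a test.
- Keep the whole-cohort result, labelled as the testing-policy contrast.
- State that a non-significant whole-cohort result is not evidence that efficacy is preserved.
- Reconcile the tested six-month PFS and OS comparison in 8.2.3(4) with the descriptive one-year OS in item 29b, including whether PFS is still analysed.

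The cost is one subset analysis plus wording. The SAP already identifies carriers and poor metabolizers in both cohorts for the TRAE contrast, and OS is already held for both. PFS in historical carriers needs extra abstraction only if it was not collected as 8.2.3(4) presumes. SAP item 14 dates the analyses to May-June 2024, so an analysis added after that should be labelled post hoc. The price is a wide interval, which shows the uncertainty openly.
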